4.4.3.3 Additional DFS and OS Analyses

In order to evaluate the robustness of the primary analyses in the event that proportionality of hazard rates may not be assumed, the following analyses may be performed for DFS and OS.

4.4.3.3.1 Restricted Mean Survival Time (RMST)

The RMST for each treatment arm may be computed for DFS and OS using the area under the corresponding survival curve from baseline to a several timepoints (e.g., 6 months, 12 months, etc.). The difference with its 95% confidence interval will be displayed.

4.4.3.3.2 Weighted Log-rank (WLR) Test

WLR test (Fine 2007) may be performed for both DFS and OS using Fleming and Harrington weight function defined at time t as: $W(t) = S(t)^\rho (1 - S(t))^\gamma$. The following two combinations of ρ and γ will be considered: $(\rho = 0, \gamma = 1)$ and $(\rho = 1, \gamma = 1)$. Both unstratified and stratified (using stratification factors mentioned in Section 4.4 analyses) will be conducted.

4.4.3.4 Biomarker Analyses

The tumor biomarkers include but are not limited to tTMB using the cut-offs of ≥ 10 mutations/MB and ≥ 16 mutations/MB separately (given data availability), PD-L1, CD8, and CD103, as defined by immunohistochemistry (IHC), quantitative reverse transcriptase-polymerase chain reaction (qRT-PCR), or other methods and would be dependent on sufficient tissue availability. Additional pharmacodynamic analyses of predictive, prognostic, and exploratory biomarkers in archival and/or fresh tumor tissue and blood and their association with disease status, mechanisms of resistance, and/or response to study treatment will be conducted as appropriate. These exploratory analyses may be provided in a separate report.

4.4.4 Sensitivity Analyses

4.4.4.1 Sensitivity Analyses on DFS for Patients in Any Treatment Arm Receiving Protocol Prohibited Anti-Cancer Therapy

The impact of protocol prohibited anti-cancer therapy on DFS may be assessed depending on the number of patients who receive such therapy before a DFS event. If $> 5\%$ of patients received protocol prohibited anti-cancer therapy before a DFS event in any treatment arm, data for these patients will be censored at the last disease assessment date before they received such therapy in DFS analyses that may be performed for the comparisons between treatment arms.

4.4.4.2 Sensitivity Analyses on OS for Patients in Observation Arm Receiving Atezolizumab or Similar Immunotherapy

The impact on OS by patients in observation arm subsequently receiving atezolizumab or another immunotherapy considered similar to atezolizumab in its mechanism of action may be assessed, depending on the number of such patients. If more than 5% of

patients in observation arm have received atezolizumab or a similar immunotherapy, the following analyses may be performed to compare treatment arms at each of the interim analyses and final analysis, as applicable:

- OS in the observation arm will be discounted according to a range of possible effects on OS after having received atezolizumab or another immunotherapy (e.g., 10%, 20%, 30%, etc.)
- Additional sensitivity analyses may be conducted if deemed necessary

4.4.5 Subgroup Analyses

The consistency of DFS results in subgroups defined by demographic, baseline disease characteristics and stratification factors will be examined. Summaries of DFS including the unstratified HR estimated from a Cox proportional hazards model and Kaplan–Meier estimates of median DFS will be produced separately for each level of the subgroup and displayed in a forest plot (Lewis and Clarke 2001). Kaplan–Meier plots of DFS will also be produced for selected subgroups.

The subgroups to be considered include but are not limited to the following:

- Age at randomization (<65 years vs. ≥65 years)
- Race (non–white vs. white)
- Sex (female vs. male)
- Region (North America, Europe, Asia, Australia)
- PD-L1 status (IC0/1 vs. IC2/3)
- Number of lymph nodes resected (<10 vs. ≥10)
- Nodal status (positive vs. negative)
- Tumor stage after resection (≤ pT2 vs. pT3/pT4)
- Prior neo–adjuvant chemotherapy (yes vs. no)
- Age-adjusted Charlson comorbidity index (ACCI) (0-1, 2-3, ≥4)
- ECOG performance status at randomization (0 vs. 1-2)
- Primary disease (MIBC vs. UTUC)
- Type of urinary diversion (ileal conduct, orthotopic, other)

Similar analyses will be performed as appropriate for OS.

4.5 SAFETY ANALYSES

Unless specified otherwise, the safety analyses described below will be conducted for the safety population (see Section 4.1.2), with patients grouped according to whether any atezolizumab treatment was received (i.e., patients who received any dose of atezolizumab will be included in the atezolizumab arm).

4.5.1 Exposure of Study Medication

Study drug exposure, including treatment duration, number of cycles, and dose intensity, will be summarized with descriptive statistics for arm A only.

4.5.2 Adverse Events

Verbatim descriptions of adverse events will be mapped to Medical Dictionary for Regulatory Activities (MedDRA terms). Treatment emergent events (defined as events occurring on or after the first dose of atezolizumab, or, for patients in the observation arm, after the date of randomization) will be summarized by MedDRA term, appropriate MedDRA levels, and NCI CTCAE (National Cancer Institute, Common Terminology Criteria for Adverse Events) v4.0 grade. For each patient, multiple occurrences of the same event will be counted once at maximum severity reported will be used in the summaries. Adverse events will be summarized regardless of relationship to study drug as assessed by the investigator. All adverse events, adverse events leading to withdrawal of study drug, adverse events leading to dose interruption, Grade ≥ 3 adverse events, serious adverse events, adverse events related to study drug, adverse events of special interest, and immune-mediated adverse events will be summarized. Deaths and cause of death will be summarized.

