5.3.1 Adverse Event Reporting Period

Investigators will seek information on adverse events at each patient contact. All adverse events, whether reported by the patient or noted by study personnel, will be recorded in the patient’s medical record and on the Adverse Event eCRF.

After informed consent has been obtained **but prior to initiation of study drug** for patients in Arm A or prior to the Cycle 1, Day 1 visit for patients in Arm B, only serious adverse events caused by a protocol-mandated intervention (e.g., invasive procedures such as biopsies, discontinuation of medications) should be reported (see Section 5.4.2 for instructions for reporting serious adverse events).

For patients in Arm A, after initiation of study drug, all serious adverse events and adverse events of special interest, regardless of relationship to study drug, will be reported until 90 days after the last dose of study drug or until the initiation of another anti-cancer therapy, whichever occurs first. All other adverse events, regardless of relationship to study drug, will be reported until 30 days after the last dose of study drug or until the initiation of another anti-cancer therapy, whichever occurs first.

For patients in Arm B, all adverse events occurring from the date of the Cycle 1, Day 1 visit until 30 days after the last day of the observation period or until the start of an anti-cancer therapy (whichever occurs first) will be reported.

Instructions for reporting adverse events that occur after the adverse event reporting period are provided in Section 5.6.

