Appendix 1 Schedule of Assessments (cont.)

- ^x After informed consent has been obtained but prior to randomization, only serious adverse events caused by a protocol-mandated intervention should be reported. Upon randomization into study, patients who experience a serious adverse event or protocol-defined adverse events of special interest will be followed for safety for 90 days following their last dose of study drug or until they receive another anti-cancer therapy, whichever comes first. Patients who experience all other adverse events will be reported for patients until 30 days after the last dose of study treatment (for Arm A) or the last day in the observation period (approximately Day 365 for Arm B), or until initiation of another anti-cancer therapy, whichever occurs first. After this period, investigators should ensure any deaths, serious adverse events, or other adverse events of concern are reported if they are later assessed to be related to atezolizumab treatment. The investigator should follow each adverse event until the event has resolved to baseline grade or better, the event is assessed as stable by the investigator, the patient is lost to follow up, or the patient withdraws consent. Every effort should be made to follow all serious adverse events considered to be related to atezolizumab treatment or trial-related procedures until a final outcome can be reported.
- ^y This clinic contact can be either via telephone call or formal clinic visit.
- ^z Survival follow-up information will be recorded via telephone calls, patient medical records, and/or clinic visits approximately every 3 months (± 7 days) from the completion or discontinuation of the treatment/observation period until death, loss to follow-up, or study termination by Roche. All patients (irrespective of which arm they are randomized to) will be followed for survival and new anticancer therapy information unless the patient requests to be withdrawn from follow-up; this request must be documented in the source documents and signed by the investigator. If the patient withdraws from study, the study staff may use a public information source (e.g., county records) to obtain information about survival status only. Patients who have completed the treatment or observation phase and continue in disease recurrence follow-up should have survival follow-up *in parallel* approximately every 3 months. All patients must still be followed for new anti-cancer therapy.

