2. STUDY DESIGN

Study WO29636 is a global Phase III, open-label, randomized, controlled trial designed to evaluate the efficacy and safety of adjuvant treatment with atezolizumab compared with observation in patients with muscle invasive urothelial carcinoma (UC), who are at high risk for recurrence following resection. The study schema is provided in [Figure 1](#).

Figure 1 Study Schema

IC = tumor-infiltrating immune cell; IV = intravenous; n = number; PD-L1 = programmed death-ligand 1; q3w = every 3 weeks; UC = Urothelial carcinoma.

Patients were randomized to one of the following arms in a 1:1 ratio:

- Arm A (experimental arm): atezolizumab 1200 mg q3w
- Arm B (control arm): observation

The randomization was stratified by the following factors: number of lymph nodes resected (< 10 vs. ≥ 10), nodal status (positive vs. negative), tumor stage after surgical resection (\leq pT2 vs. pT3/pT4), PD-L1 status (IC0/1 vs. IC2/3), and prior neo–adjuvant chemotherapy (yes vs. no).

Note: The study design was revised in Protocol Version (v) 6 from a diagnostically selected population with PD–L1 status (tumor–infiltrating immune cell [IC] score measured in tumor) of IC2/3 to include all patients regardless of PD–L1 status. Age–adjusted Charlson comorbidity index, which was a stratification factor prior to Protocol v6, was removed as a stratification factor in Protocol v6 and replaced with PD–L1 status (IC0/1 vs IC2/3). Patients enrolled prior to Protocol v6 have been categorized as IC2/3 for stratification purposes.

For patients in Arm A, atezolizumab will be administered intravenously (IV) on Day 1 of each 21-day cycle for 16 cycles (up to 1 year). In Arm B, patients will continually undergo observation starting on Day 1 of each 21-day cycle for 16 cycles (up to 1 year).

Treatment/observation will be discontinued in the event of disease recurrence, unacceptable toxicity, withdrawal of consent, or study termination by the Sponsor. Patients in the control arm will not be allowed to cross over to receive atezolizumab treatment within this study.

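### Adverse-event collection stops at different times in the two arms and the SAP tabulates only crude patient counts, so the percentages can differ by a few points with identical true event rates.

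*SAP*

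**What the plan says.** **Collection in Arm A.** Protocol 5.3.1 ties the window to the last dose. Serious events and events of special interest, "regardless of relationship to study drug, will be reported until 90 days after the last dose of study drug". For the rest: "All other adverse events, regardless of relationship to study drug, will be reported until 30 days after the last dose of study drug". Both windows close early if another anti-cancer therapy starts.

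**Collection in Arm B.** There is one window for all events, serious or not: "all adverse events occurring from the date of the Cycle 1, Day 1 visit until 30 days after the last day of the observation period". It too closes early if an anti-cancer therapy starts. Protocol 4.6.2 and 5.4.2.2 give the same 30-day tail. Appendix 1, footnote x, refers instead to "the last day in the observation period (approximately Day 365 for Arm B". The 30-day tail in that sentence may or may not apply to Arm B. The footnote also counts serious-event follow-up only from the last dose, which Arm B does not have.

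**Planned duration.** SAP 2 has both arms running from "Day 1 of each 21-day cycle for 16 cycles (up to 1 year".

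**Analysis.** SAP 4.5.2 begins its definition with "Treatment emergent events (defined as events occurring on or after the first dose of atezolizumab, or, for patients in the observation arm" and gives no closing date. A patient with several occurrences of an event counts once, at maximum severity. No person-time rate or time-to-first-event summary is planned. SAP 4.5.1 limits exposure summaries to Arm A. Protocol 6.5 promises length of safety follow-up by arm, but SAP 4.5 does not repeat it, and SAP 1 says the SAP's analyses supersede the protocol's. SAP 4.2 summarizes length of follow-up for the ITT population, which is not the time during which adverse events were collected.

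**The concern.** A crude percentage of patients with an event grows with the time over which events are collected. Here that time is set by a different anchor in each arm, and it is cut short in Arm A by toxicity stops, which in effect have no Arm B counterpart. Observation is the only concurrent reference for the objective of describing tolerability in the adjuvant setting. If the adverse-event tables show Arm A somewhat lower for other events, or somewhat higher for serious ones, a reader cannot tell how much of that is the drug and how much is the calendar.

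**Working it through.** **Plan's own figure.** The plan states no safety precision or adverse-event difference. The one design input used here, the 20-month DFS median, is consistent with the event target: 4 × (1.960 + 0.842)² / [ln(20/26.7)]² = 31.40 / 0.0835 = 376.1, which rounds up to the stated 377.

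**Windows for an on-schedule completer**
- Arm A last dose, Cycle 16 Day 1: 1 + 15 × 21 = Day 316. Other events end at 316 + 30 = Day 346; serious events and events of special interest at 316 + 90 = Day 406.
- Arm B, all events: 365 + 30 = Day 395 if Protocol 5.3.1 and Appendix 1 are combined; Day 365 if footnote x means no tail; Day 346 if the last observation day is taken as Cycle 16 Day 1 (316 + 30). The last sits poorly with the footnote's Day 365 and is kept as a bound.

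**Window for a toxicity stop at Cycle 4.** Last dose on Day 1 + 3 × 21 = 64; other events end at Day 94 and serious events at Day 154. A comparable Arm B patient stays in collection to the end.

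**Completers, equal hazards.** P(at least one event) = 1 - exp(-λ × days), with λ = 0.35/365.25 per day (assumed) and the day number taken as the window length: Day 346, 28.2%; Day 365, 29.5%; Day 395, 31.5%; Day 406, 32.2%. Arm A minus Arm B:

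| Arm B ends | Other events | Serious events |
|---|---|---|
| Day 395 | 28.2 - 31.5 = -3.3 | 32.2 - 31.5 = +0.7 |
| Day 365 | 28.2 - 29.5 = -1.3 | 32.2 - 29.5 = +2.7 |
| Day 346 | 0 | 32.2 - 28.2 = +4.0 |

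**All patients.** Simulation, 2,000,000 per arm, same constant event hazard in both arms, exponential recurrence with a 20-month median in both arms, toxicity stops in Arm A only, windows closed at new therapy. With a 30% one-year risk and a mean of 60 days from recurrence to new therapy, Arm A minus Arm B in points:

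| Toxicity stops | Arm B ends | Other events | Serious events |
|---|---|---|---|
| 6% | Day 395 | -3.0 | +0.5 |
| 6% | Day 365 | -1.0 | +2.5 |
| 6% | Day 346 | -0.7 | +2.8 |
| 15% | Day 395 | -3.8 | -0.2 |
| 15% | Day 365 | -1.8 | +1.8 |
| 15% | Day 346 | -1.5 | +2.0 |

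With 0.35 per patient-year (one-year risk 1 - exp(-0.35) = 29.5%), new therapy 45 days after recurrence and 0-15% toxicity stops, the Day 395 reading gives -2.5 to -4.1 points for other events and -0.6 to +0.9 for serious events. Under the earlier ends, other events are about 0-3 points lower in Arm A and serious events up to about 3 points higher.

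**Sensitivity.** At a 50% one-year risk with 25% toxicity stops and the Day 395 reading, other events reach -7.1. In the other direction, dosing delays lengthen the Arm A window: with 5.9% stops and an assumed mean cumulative delay of 14-21 days, the Day 395 figures become -2.5 to -2.1 for other events and +0.9 to +1.2 for serious events.

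**Source of the assumptions.** The documents give no event rate or toxicity-stop rate for this population. Protocol 1.2.2.2 reports 5.9% and 2.9% stopping for adverse events and 36.1% and 46.1% with a serious event, all in metastatic cohorts and for orientation only.

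**The case against.** The strongest reply is that SAP 4.5.2 summarizes and does not test. No between-arm estimate or decision rule hangs on these tables, events of special interest are reported for Arm A only, and Protocol 6.5 plans length of safety follow-up by arm, so unequal windows would be visible. The first two parts stand and limit the weight of the point. The third is weaker, because the SAP supersedes the protocol's analyses and does not carry that summary into its safety section.

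Three stronger readings are tempting, and the documents do not support them.

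- *Serious and other events are distorted in opposite directions.* Under the Day 395 reading even the sign for serious events is unsettled. A clear excess in Arm A needs an earlier Arm B end.
- *Grade 3 or higher events are under-counted in Arm A.* Those that are serious or of special interest have the 90-day tail in Arm A and the rest have 30 days. Protocol Table 8 puts hospitalization within Grade 3 and requires Grade 5 to be reported as serious. The class mixes both windows, and its direction has not been worked out.
- *After recurrence, serious events have 90 days in Arm A against 30 in Arm B.* Both windows also close at new therapy. With new therapy 45 days after recurrence the gap is about 45 - 30 = 15 days, not 60.

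The sentence quoted from SAP 4.5.2 concerns the start of the period, where the arms differ by at most the 7 days allowed between randomization and first dose. Its relevance is that it sets no end; the unequal ends come from Protocol 5.3.1 and Appendix 1.

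**Conclusion.** The point holds in a limited form. The collection windows differ by arm, and the SAP's crude counts do nothing to allow for it. With identical hazards, other adverse events would appear about 2.5-4 points lower in Arm A if Arm B runs to about Day 395, and about 0-3 points lower if it ends between Day 346 and Day 365. For serious events the artefact is roughly -0.6 to +0.9 points under Day 395 and up to about +3 points in Arm A under the earlier ends. The direction for Grade 3 or higher events overall is undetermined.

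These sizes rest on assumed values: a constant 0.35 events per patient-year, a 20-month DFS median in both arms, new therapy at 45 days after recurrence, 0-15% toxicity stops, and dosing on schedule. Delays would shrink the figure for other events. That the windows are unequal is a matter of the text and needs none of these assumptions.

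**What to change.** In SAP 4.5.2, keep the crude tables and add, by arm:

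1. Length of adverse-event collection, separately for serious and other events.
2. Exposure-adjusted incidence rates for all, Grade 3 or higher and serious events: first events per patient-year of collection, with the patient-years taken from the window for each class. A 30% one-year risk is -ln(0.70) = 35.7 per 100 patient-years in both arms, whatever the window. State that this removes the artefact exactly only if the hazard is roughly constant.
3. A serious-event table with the same 30-day tail in both arms, and Arm A days 31-90 after last dose shown separately. This equalizes the tail, not the anchor: a Cycle 4 toxicity stop is still cut at Day 94. The rates must therefore carry the comparison.

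Reconcile Protocol 5.3.1 with Appendix 1, footnote x, on when the Arm B window ends, and give that end date in the SAP definition.

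The cost is SAP wording and a few extra tables from data already collected.
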